7.1 Safety parameters

The safety parameters of this study include clinical symptoms, vital signs, physical examination, and laboratory tests (such as complete blood count, biochemical tests, and coagulation function). The study evaluates adverse events according to the National Cancer Institute (NCI) Common Terminology Criteria for Adverse Events (CTCAE) version 6.0 (https://ctep.cancer.gov/protocoldevelopment/electronic_applications/ctc.htm),

including the type, incidence, severity, onset and resolution time, whether they are serious, their relevance to the study treatment, and their outcomes.

7.2 Definition of adverse events

Adverse events refer to any adverse medical outcomes experienced by patients or clinical trial participants after taking the medication, which may not necessarily be causally linked to the treatment. Therefore, adverse events can include any adverse and other unexpected physical signs (including abnormal laboratory findings) and symptoms, as well as diseases that are temporally associated with the use of the medical product, regardless of whether they are considered related to the study drug. These events must at least include the following:

- Worsening of the original (pre-clinical) medical condition/disease (including worsening of symptoms, signs or laboratory abnormalities);
- Any new medical condition (including symptoms, signs or newly diagnosed disease);
- Abnormal clinically significant laboratory test values or results.

7.3 Definition of serious adverse events

Serious adverse event is any adverse medical condition that occurs at any dose that meets one of the following criteria:

- Fatality (resulting in death; Note: death is a consequence, not an event);
- Life-threatening ("life-threatening" means that the patient is immediately at risk of death at the time of the event, not that death would be caused by a more serious event);
- Resulting in hospitalization or prolonged hospital stay;
- Causing lifelong or severe disability/functioning impairment;
- Causing birth defects or birth defects;
- Of medical significance or requiring intervention to prevent any of these outcomes.

Tumor progression or deterioration (including the appearance of new metastases and death due to disease progression) that occurs during the course of the study should be part of the efficacy evaluation and should not be reported as an adverse event or serious adverse event.

7.4 Definition of serious adverse events

Disease progression is defined as the deterioration of a subject's condition due to the study's indications. This includes both imaging and clinical symptom and sign advancements. The appearance of new metastases relative to the primary tumor or the progression of existing metastases is considered disease progression. Life-threatening symptoms and signs resulting from disease progression, requiring hospitalization or extended hospital stays, or leading to permanent or severe disability affecting work capacity, are not reported as serious adverse events. However, deaths caused by symptoms and signs due to disease progression are reported as Serious Adverse Events (SAE).

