2.3 Study endpoints

Main endpoints and definitions:

This study primarily evaluates the proportion of patients with YWHAB

high expression locally advanced rectal cancer who achieve tumor downstaging (ypTNM 0-I stage) after neoadjuvant therapy with mFOLFOX6 combined with Citrus Flavonoid Tablets (Aimianlang). The tumor downstaging rate (ypTNM 0-I stage) refers to the percentage of patients with locally advanced rectal cancer who, after receiving neoadjuvant chemotherapy with mFOLFOX6 or mFOLFOX6 + Citrus Flavonoid Tablets (Aimianlang), have their postoperative pathological stage of the surgical specimen classified as ypTNM 0-I stage.

Secondary endpoints and definitions:

- (1) The degree of pathological remission is defined as follows: ① Complete Remission (CR): All tumor target lesions have disappeared, no new lesions have appeared, and tumor markers are normal, lasting at least 4 weeks. ② Partial Response (PR): The sum of the maximum diameters of tumor target lesions has decreased by at least 30%, lasting at least 4 weeks. ③ Stable Disease (SD): The sum of the maximum diameters of tumor target lesions has not decreased by more than PR, or increased by less than PD. ④ Disease Progression (PD): The sum of the maximum diameters of tumor target lesions has increased by at least 20%, or new lesions have appeared.
- (2) The 3-year disease-free survival rate (DFS) is the proportion of patients who have not experienced any of the following events from the start of randomization to the end of year 3: disease progression, surgical gross/microscopic tumor residue, local recurrence, distant metastasis, or death for any reason, whichever occurs first.
- (3) Overall survival time (OS) is the time from randomization to death for any reason.
- (4) Tumor regression grading TRG: TRG 0 means no residual tumor cells, TRG 1 means a single cell or a small group of cells; TRG 2 means residual cancer with a proliferative response to connective tissue; TRG 3 means minimal evidence of tumor response.
- (5) Safety indicators, treatment-related adverse reaction rate (grade III and

above): Antitumor drugs/therapy In clinical trials, drug adverse reactions determined to be related to drug therapy at grade III and above, excluding nonspecific infusion reactions.

3. Selection and withdrawal of subjects

3.1 Inclusion criteria:

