The main efficacy indicator of this study was the proportion of patients in each treatment group who achieved tumor downstaging (ypTNM 0-I stage), and the secondary efficacy indicators were the proportion of patients with complete pathological remission, 3-year disease-free survival (DFS), overall survival time (OS) and tumor regression grade TRG.

6.2 Evaluation criteria of effectiveness:

This study evaluated the proportion of patients with YWHAB high expression locally advanced rectal cancer who achieved tumor downstaging (ypTNM 0-I stage) in neoadjuvant treatment with mFOLFOX6 combined with citrus flavonoid tablets (Aimalang).

- (1) Downstaging rate of tumor (ypTNM 0-I stage): the proportion of patients with locally advanced rectal cancer who received mFOLFOX6 or mFOLFOX6 combined with citrus flavonoid tablets (Aimalang) as neoadjuvant chemotherapy, and the proportion of patients with postoperative pathological stage of ypTNM 0-I stage in surgical specimens.
- (2) The degree of pathological remission is defined as follows: ① Complete Remission (CR): All tumor target lesions have disappeared, no new lesions have appeared, and tumor markers are normal, lasting at least 4 weeks. ② Partial Response (PR): The sum of the maximum diameters of tumor target lesions has decreased by at least 30%, lasting at least 4 weeks. ③ Stable Disease (SD): The sum of the maximum diameters of tumor target lesions has not decreased by more than PR, or increased by less than PD. ④ Disease Progression (PD): The sum of the maximum diameters of tumor target lesions has increased by at least 20%, or new lesions have appeared.

Subjects who did not meet the primary endpoint criteria are included in the denominator but not in the numerator.

- (3) When determining the disease-free survival (DFS), clinical deterioration without clear evidence of disease progression according to the RECIST 1.1 criteria is not considered a disease progression. For subjects who died without prior reported disease progression, it is considered that the disease progressed at the time of death. Subjects who have neither experienced disease progression nor died will be censored at their last evaluable tumor evaluation date. Independent central imaging review will be conducted to confirm the independent central imaging service provider of the subject, which will receive all images from the research center and assess the subject's disease progression according to the RECIST 1.1 criteria.

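### Progression judged on clinical grounds is exempt from SAE reporting because it belongs to efficacy, yet DFS does not accept it without RECIST 1.1 evidence, so a serious non-fatal event can be missing from both

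*Combined protocol and SAP*

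**What the plan says.** Five parts of the combined protocol and SAP bear on this point.

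- **7.2 (adverse events)** gives a minimum list of what counts as an AE. It includes "Worsening of the original (pre-clinical) medical condition/disease", covering symptoms and signs.
- **7.3 (serious adverse events)** says that tumour progression or deterioration "should be part of the efficacy evaluation and should not be reported as an adverse event or serious adverse event".
- **7.4** carries the same heading as 7.3 but defines disease progression: "This includes both imaging and clinical symptom and sign advancements". It then lists life-threatening symptoms, hospitalisation and consequences "leading to permanent or severe disability affecting work capacity, are not reported as serious adverse events". Deaths from progression are kept as SAEs.
- **6.2(3) (DFS)** says that "clinical deterioration without clear evidence of disease progression according to the RECIST 1.1 criteria is not considered a disease progression". Images go to independent central review under RECIST 1.1. The censoring rule reads: "Subjects who have neither experienced disease progression nor died will be censored at their last evaluable tumor evaluation date".
- **2.3(2) (DFS events)** lists "disease progression, surgical gross/microscopic tumor residue, local recurrence, distant metastasis, or death for any reason, whichever occurs first". Clinical progression has no entry of its own.

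**The concern.** An exemption of progression from safety reporting is sound only if the efficacy data capture what is exempted. Here the two sides use different definitions. Safety exempts progression judged on imaging or on clinical grounds. DFS accepts progression only with RECIST 1.1 evidence. Events that fall between the two definitions are passed to an endpoint that does not take them.

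Two things are at stake. The first is completeness of the SAE listing, and possibly of the all-cause AE summaries, including the 24-hour report under 7.6.2. The second is bias. The trial is open-label, so whoever decides that an event is due to the cancer rather than to treatment knows the arm. That decision could differ between arms, and censoring a patient who has just deteriorated is likely to be informative for DFS. The documents do not show which way either effect would run.

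**Working it through.** The plan states no figure on this point, so the check is a comparison of rules, case by case.

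**Step 1: classify each type of event under the rules as written.**

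| Event | SAE | AE | DFS |
|---|---|---|---|
| (a) Progression with RECIST 1.1 evidence | No (7.3, 7.4) | No (7.3); yes (7.2) | Event |
| (b) Death due to progression | Yes (7.4); no (7.3) | No (7.3) | Event, as any-cause death |
| (c) Clinical deterioration, later confirmed by RECIST or by another 2.3(2) event | No (7.3, 7.4) | No (7.3); yes (7.2) | Event, dated at the confirming finding |
| (d) Serious, non-fatal clinical deterioration attributed to the cancer and never confirmed | No (7.3, 7.4) | No (7.3); yes (7.2) | No event; censored at last evaluable tumour evaluation |

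Cases (a) to (c) are all captured in DFS. Case (d) is not captured in DFS or in the SAE listing. Whether it appears as an AE depends on whether the site follows 7.2 or 7.3.

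**Step 2: see whether other provisions rescue case (d).**

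- 5.2 permits unscheduled imaging when symptoms worsen but does not require it. Scheduled imaging in the treatment period is after cycles 6 and 12.
- 5.4 asks sites to try hard to obtain imaging evidence of progression. It also ends scheduled imaging once other anti-tumour treatment starts, so a patient switched on clinical grounds may never be confirmed.

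These provisions narrow the gap without closing it.

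**Step 3: fix the time window.** Under 7.6.1, AEs are collected to 30 days after the last study drug. Unrelated SAEs are collected to 90 days, or to the start of new anti-tumour treatment if that is earlier. After that, an event attributed to the cancer would not be collected under any reading of 7.3 and 7.4. The double loss can therefore arise only on treatment and shortly afterwards.

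**Step 4: trace the effect on each outcome for a patient in case (d).**

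- *Primary endpoint:* the patient stays in the ITT set (8.1). Under 6.2, a patient who does not reach ypTNM 0-I remains in the denominator as a failure.
- *OS:* unaffected.
- *DFS:* censored, and visible in the table of censored cases by reason (8.3), but without an event.
- *Grade III and above treatment-related rate (2.3(5)):* limited effect. The exemption acts before causality is assessed. Under 7.5.2, an event with plausible timing that the disease might also explain meets the two required criteria for the may-be-related category. Only events that would have been placed there could have entered this rate.
- *SAE listing and all-cause AE summaries (8.4):* the SAE is missing; the AE is missing if 7.3 is followed.

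**The case against.** The strongest reply is that the gap is narrow and that 7.2 already covers it. 7.2 makes worsening of the original disease an AE. The phrase in 7.3 can be read as worsening of the tumour itself rather than of every symptom attributed to it. 7.4 on its own removes such events only from SAE reporting. A site reading the text this way would record and grade an obstruction or a bleed. Patients are M0 at entry, and those needing emergency surgery for complete obstruction, active bleeding or perforation are excluded. Many deteriorations will be imaged, or will lead to surgery where residual tumour is itself a DFS event. Safety analysis is descriptive, so no formal test is affected.

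Most of this stands as a limit on size. It does not remove the defect: on the reading most favourable to the plan, case (d) is still missing from the SAE listing and is still not a DFS event. The conflict between 7.2 and 7.3 also means that sites could classify identical events differently.

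A reader might infer three stronger things, which the documents do not support:

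- *That such patients leave every outcome table.* They stay in the primary analysis, in OS and among the tabulated DFS censorings.
- *That serious events generally vanish from the grade III and above rate.* That endpoint counts only reactions judged related to drug therapy, and an event attributed to the cancer would mostly be judged unrelated.
- *A number of patients lost.* Assuming 2% to 5% of the 236 planned patients gives 0.02 × 236 = 4.7 to 0.05 × 236 = 11.8, but nothing in the documents supports that range or rules out a value near zero. Assuming 2% in one arm and 5% in the other, and so a hidden 3-point difference in SAEs, adds a second unsupported assumption.

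**Conclusion.** The plan is wrong as written on this point. Following 7.3, 7.4 and 6.2(3) literally, a serious non-fatal deterioration can be missing from the SAE listing and be no event in DFS. It is also missing from the all-cause AE summaries where 7.3 is followed over 7.2.

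This holds only if all of the following apply: the event is non-fatal; it falls within the safety-collection window; the investigator attributes it to the cancer; and neither RECIST 1.1 evidence nor another 2.3(2) event ever follows. Its frequency cannot be estimated from the documents, and neither can the size of any difference between arms. The primary analysis and OS are not affected. The conclusion rests on the wording of the rules and on no assumed rate.

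The separate conflict between 7.3 and 7.4 over whether deaths from progression are SAEs should be settled in the same revision, but settling it alone would leave this gap open.

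**What to change.** Reconcile 7.2, 7.3, 7.4 and 6.2(3) so that every such event is recorded in at least one place:

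1. In 7.3 and 7.4, limit the reporting exemption to progression documented by RECIST 1.1 evidence under 6.2(3), or by another event listed in 2.3(2).
2. State that any other deterioration meeting a seriousness criterion in 7.3 is recorded as an AE, graded, assessed for causality under 7.5.2 and reported as an SAE under 7.6.2.
3. Align the item on worsening of the original disease in 7.2 with this wording.

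The DFS definition need not change, because the event is then captured in safety. A DFS sensitivity analysis counting clinical progression as an event would be a useful optional addition. It would show whether the censoring matters.

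The cost is a short protocol revision and a few more SAE reports, with no extra patients or procedures. It is best made before enrolment, because events that were never reported may be hard to reconstruct and re-attribute later.

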7.5 Classification of adverse events and serious adverse events

7.5.1 Criteria for judging the severity of adverse events:

The severity of adverse events will be graded using NCI CTCAE version 6.0 and reported in detail as required on the CRF. If an adverse event is not included in NCI CTCAE version 6.0, the following five-level classification will be used:

- Mild: no clinical symptoms or mild clinical symptoms; only clinical or laboratory abnormalities; no treatment is required.
- Moderate: Requires minor, localized or non-invasive treatment; limited use of tools and other daily activities consistent with age.
- Severe; serious or medically severe symptoms that are not life-threatening at the time of presentation; hospitalization or prolonged hospital stay; disability; and limited ability to perform activities of daily living.

- Life-threatening; immediate life danger and urgent medical treatment is required
- Death: Death associated with adverse events.

7.5.2 Judgment of the relationship between adverse events and study treatment

The following criteria should be used to assess the relationship between adverse events and treatment:

- It is likely to be relevant (must have the first three): This category refers to adverse events for which there is a high degree of certainty that they are related to the investigational drug. An adverse event may be considered "likely to be relevant" if the following criteria are met:
 1. The occurrence of adverse events is associated with the use of drugs in a reasonable time.
 2. The known patient disease status, environmental or toxic factors or other treatments used by the patient do not reasonably explain the adverse event.
 3. After the dose is stopped or reduced, the adverse reactions will disappear or be alleviated. (However, there are some important exceptions, some drug-related adverse reactions will not disappear even after the drug is stopped; such as: (1) bone marrow suppression, (2) delayed motor dysfunction)
 4. The adverse events were consistent with the pattern of suspected drug reactions.
 5. When used again, the adverse event reappeared.
- May be related (must have the first two): This category refers to adverse events that are unlikely to be related to the administration of the investigational drug but cannot be definitively excluded from association. An adverse event may be considered "may be related" if the following criteria are met:

1. The occurrence of adverse events is associated with the use of drugs in a reasonable time.
2. Adverse reactions may be caused by the patient's disease status, environment or toxic factors or other concomitant treatments used by the patient.
3. The adverse events were consistent with the pattern of suspected drug reactions.

- May be irrelevant (must have the first two): This category applies to adverse events that meet the following criteria:
 1. The occurrence of adverse events is not reasonably time-related to drug use.
 2. Adverse events were clearly caused by the patient's disease status, environment or toxic factors or other concomitant treatments used by the patient.
 3. The adverse events did not conform to the pattern of suspected drug reactions.
 4. When the drug was used again, the adverse events did not occur or worsen.
- Irrelevant: This category refers to adverse events that are clearly and definitively judged to be caused only by external factors (disease, environment, etc.) and do not meet the criteria for drug-relatedness under "probably irrelevant", "probably related" or "likely related".

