2.2 Research purpose

Main research objectives:

To evaluate the proportion of patients achieving tumor downstaging (ypTNM 0-I stage) in YWHAB high-expressing locally advanced rectal cancer treated with mFOLFOX6 combined with Citrus Flavonoid Tablets (Aimalang) as a neoadjuvant therapy, to provide evidence that Citrus Flavonoid Tablets (Aimalang) enhances the effectiveness of the mFOLFOX6 regimen in this patient population.

Secondary study objectives:

Efficacy evaluation: The proportion of pathological complete remission, 3-year disease-free survival (DFS), overall survival time (OS) and tumor regression grade TRG were evaluated in patients with YWHAB high expression locally advanced rectal cancer treated with mFOLFOX6 combined with citrus flavonoid tablets (Aimalang) as neoadjuvant therapy.

Safety evaluation: The treatment-related adverse reaction rate (grade 3 or above) of mFOLFOX6 combined with citrus flavonoid tablets (Aimalang) regimen for neoadjuvant treatment of YWHAB high expression local advanced rectal cancer patients was evaluated.

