7.6 Follow-up and reporting of adverse events

7.6.1 Collection and follow-up of adverse events/severe adverse events:

The collection period of adverse events starts from the date of signing the informed consent form by the subject and ends 30 days after the last study drug.

The collection period of serious adverse events begins with the signing of informed consent by the subject. For serious adverse events unrelated to the study drug, the collection period is 90 days after the last study drug or the start of new anti-tumor treatment (whichever comes first); after that, only serious adverse events related to the study drug will be collected.

Follow-up for adverse events or serious adverse events should continue until the event resolves, is alleviated to baseline levels or ≤ 1 level, reaches a stable state, or is reasonably explained (such as loss to follow-up or death). The best possible outcome should be sought. Researchers should inquire about any adverse events or serious adverse events that have occurred since the last visit during each follow-up visit and provide timely follow-up information as requested by the sponsor.

7.6.2 Reporting of serious adverse events:

During the study, regardless of the treatment received by the patient, any serious adverse events or serious laboratory test results that occur must be reported by the investigator to the CFDA Serious Adverse Event Report Form

and the adverse event report form, and reported to the designated contact within 24 hours of learning:

Contact person for serious adverse event reporting: GCP Office, Sixth Affiliated Hospital of Sun Yat-sen University

Contact person of the research group leader: [name] (The Sixth Affiliated Hospital of Sun Yat-sen University)

Email: [contact]

Address: [name]

The contact person for serious adverse event reporting should, within one working day of receiving a report from a researcher, fax the signed form to the lead unit. The report must adhere to the guidelines and standards set by the International Council for Harmonization (ICH) for the management of safety data in clinical trials and the definition of rapid reporting.

7.6.3 Reporting of non-serious adverse events:

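### The grade III+ treatment-related endpoint has no neoadjuvant time window, and the causality rules behind it leave some reactions without a clear category

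*Combined protocol and SAP*

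**What the plan says.** **Objective and endpoint.** The safety objective in Section 2.2 is "The treatment-related adverse reaction rate (grade 3 or above) of mFOLFOX6 combined with citrus flavonoid tablets (Aimalang) regimen for neoadjuvant treatment" of YWHAB-high locally advanced rectal cancer. Section 2.3, secondary endpoint (5), counts "drug adverse reactions determined to be related to drug therapy at grade III and above, excluding nonspecific infusion reactions". It gives no start or end date and does not say which causality categories amount to related.

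**Periods.** Section 4.1 plans 4–6 cycles before surgery and 6–8 after. It leaves postoperative treatment in both groups to the investigator and allows it to include the tablets. Section 5.2 runs the treatment period from first dose until study treatment is discontinued. Section 7.6.1 starts adverse-event collection at consent, and it "ends 30 days after the last study drug". Section 8.4 tabulates events during treatment by worst grade, with no split at surgery.

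**Causality (Section 7.5.2).** There are four categories:

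- *Likely*: "It is likely to be relevant (must have the first three" of five criteria. These are plausible timing, that disease, environment or "other treatments used by the patient do not reasonably explain the adverse event", and "After the dose is stopped or reduced, the adverse reactions will disappear or be alleviated". A bracketed note says that some reactions persist after stopping and gives two examples.
- *May be related*: plausible timing and a possible other cause are both mandatory. The category is described as "adverse events that are unlikely to be related to the administration of the investigational drug but cannot be definitively excluded from association".
- *May be irrelevant*: no plausible timing and a clear other cause are both mandatory.
- *Irrelevant*: definitely due only to external factors, and not meeting the criteria of the other categories.

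**The concern.** This is the only named safety endpoint, and it should show whether adding the tablets to neoadjuvant mFOLFOX6 raises serious toxicity. Two things stand in the way.

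First, the objective covers the preoperative phase, while everything that feeds the rate continues through surgery and the postoperative cycles. The primary benefit is read from the surgical specimen, so benefit and harm would cover different periods.

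Second, the endpoint depends on a relatedness judgment made by investigators who know the arm (Section 2.1: open design). The scale they use has a gap where a drug reaction is most plausible. Its middle category carries a label and a description that point in opposite directions. Two analysts could include or exclude that whole category and both would be following the protocol.

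The classification also affects collection. Under Section 7.6.1, serious events unrelated to study drug stop being collected 90 days after the last dose or when new anti-tumour treatment starts, whichever comes first. After that only related ones are kept, so an event without a category has no defined handling.

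**Working it through.** The plan states no figure on this point, so there is none to reproduce. The check sets the sections side by side and applies the causality criteria literally.

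**Step 1: does any section cut the endpoint at surgery?**

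| Element | Section | Ends at |
|---|---|---|
| Objective | 2.2 | Neoadjuvant treatment |
| Endpoint | 2.3(5) | Not stated |
| Treatment period | 5.2 | Discontinuation of study treatment |
| Collection | 7.6.1 | 30 days after last study drug |
| Tables | 8.4 | Events during treatment, worst grade |

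Only the objective is limited to the preoperative phase. Section 5.2 also lists imaging after 12 cycles within the treatment period. With at most 6 preoperative cycles, that point is reached only after surgery.

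**Step 2: how much of the planned course is postoperative?** Share = postoperative cycles / all planned cycles (Section 4.1).

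- 6 + 6: 6/12 = 50%
- 6 + 8: 8/14 = 57%
- 4 + 6: 6/10 = 60%
- 4 + 8: 8/12 = 67%

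The range is 50–67% of planned cycles. This is not delivered exposure, which will be lower after surgery for anyone who stops early or receives something else.

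**Step 3: is there a category for every event?** Cross three features: plausible timing (yes, no); other cause (none, possible, clear and only external); response to stopping or reducing the dose (improved; not improved or not tested; not improved but of a type the bracketed note excepts). This gives 2 × 3 × 3 = 18 combinations.

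- Plausible timing, no other cause, not improved or not tested, not an excepted type. *Likely* fails on criterion 3. *May be related* fails because no other cause exists. *May be irrelevant* fails on timing. *Irrelevant* fails because there is no external cause. The result is no category under every reading.
- The same event, but of an excepted type. It is *likely* if the note waives criterion 3, and has no category if it does not. The note never says that it waives the criterion.
- No plausible timing, with either no other cause or only a possible one. These 2 × 3 = 6 combinations have no category under any reading.

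Total without a category: 1 + 6 = 7 of 18 if the note waives criterion 3, and 2 + 6 = 8 of 18 if it does not. These count logical combinations, not patients. The six without plausible timing matter little for a treatment-related rate. The one or two with plausible timing matter: examples are a fatal reaction, or one where dosing continued unchanged.

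**Step 4: which categories count?** Section 2.3(5) requires a determination that the reaction is related. Section 8.4 promises treatment-related tables. Neither says whether *may be related* qualifies.

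**Step 5: scale.** No section gives a grade III+ rate, so the shift cannot be computed. For scale only, assume that the 236 patients are split equally, all are treated, and the rate is a proportion of patients. Each reclassified patient then moves an arm's rate by 1/118 = 0.85 percentage points. How many would be reclassified is unknown.

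**The case against.** The strongest reply is that little is lost. The endpoint is secondary, Section 8.4 limits safety to descriptive summaries, and no test or sample size depends on it. Serious events are reported whatever their cause (Section 7.6.2), and all-cause tables are planned. All of this stands, and it rules out one tempting inference: that the worst reactions would vanish from reporting. They would still be reported. What is unsettled is whether they enter the named endpoint.

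A second reply is that the note to criterion 3 is open-ended and lets an investigator classify a persistent reaction as *likely*. That is a fair reading and narrows the gap, but the text does not state it.

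A third is that the objective already says neoadjuvant and Section 8.4 leaves detail to the statistical analysis plan. The combined document adds nothing that sets a window, and a collection period is not an endpoint window.

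A reader might also infer that a clearly surgical complication with plausible timing must be labelled *may be related*. The documents do not support that. Section 7.5.2 distinguishes events that may have another cause from those that clearly do, and it provides *irrelevant* for events due only to external factors. The wording leaves room for the wrong label but does not require it.

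Nor do the causality categories create the window problem, since Section 7.5.2 sets no period. The mismatch lies between Section 2.2 and Sections 2.3(5), 5.2, 7.6.1 and 8.4.

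Finally, stopping the window at surgery could hide complications that matter. Section 1 itself cites anastomotic leakage as a difference between neoadjuvant approaches. That is a good reason to report perioperative events in their own table.

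**Conclusion.** The point holds in two parts. First, the reported rate would pool postoperative events into a figure meant to describe neoadjuvant treatment, with 50–67% of planned cycles falling after surgery. Second, a well-timed, otherwise unexplained reaction that does not improve has no clear category, and the status of *may be related* is undefined.

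The effect on the rate cannot be sized from the documents. The 50–67% rests on planned cycles, and the 0.85 points per patient on equal allocation of 236 treated patients. No error rate or sample size changes. The wording should still be settled before data are seen, because relatedness is judged with the arm known.

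**What to change.** 1. **Sections 2.3(5) and 8.4.** Report the grade III+ treatment-related rate by arm for the neoadjuvant period: first dose to surgery, or to 30 days after the last preoperative dose if there is no surgery. Tabulate perioperative events and postoperative-cycle events separately. Show the all-cause grade III+ rate for the same periods and arms beside each.
2. **Section 7.5.2.** Make criterion 3 supportive rather than mandatory for *likely*. Delete the statement that *may be related* events are unlikely to be related.
3. **Section 2.3(5).** State that *likely* plus *may be related* count as treatment-related.

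Item 2 closes every gap with plausible timing. The six combinations without plausible timing remain (7 − 1 or 8 − 2 = 6), but they do not bear on a treatment-related rate. There is no need for a rule sending every clearly surgical event to *irrelevant* whatever its timing. Such a rule would empty *may be irrelevant*, which requires a clear other cause.

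The cost is one table split and some protocol and CRF wording. The related rate may look slightly less favourable.
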